1. ETHICS

1.1. Institutional Review Board (IRB)/Independent Ethics Committee (IEC)

It is the responsibility of the investigator to have prospective approval of the study protocol, protocol amendments, informed consent forms, and other relevant documents, e.g., recruitment materials, if applicable, from the IRB/IEC. All correspondence with the IRB/IEC should be retained in the Investigator File (Site Master File). Copies of IRB/IEC approvals should be forwarded to the Sponsor.

The only circumstance in which a protocol amendment may be initiated prior to IRB/IEC approval is where the change is necessary to eliminate apparent immediate hazards to the subjects. In that event, the investigator must notify the IRB/IEC and the Sponsor in writing within 5 working days after the implementation.

1.2. Ethical Conduct of the Study

The study will be performed in accordance with the protocol, International Conference on Harmonization Good Clinical Practice guidelines (ICH E6-R2) and applicable local regulatory requirements and laws.

1.3. Subject Information and Consent

All parties will ensure protection of subject personal data and will not include subject names on any forms, reports, publications, or in any other disclosures. In case of data transfer, Sponsor will maintain high standards of confidentiality and protection of subject personal data.

The informed consent form must be agreed to by the Sponsor and the IRB/IEC and must be in compliance with ICH GCP, local regulatory requirements, and legal requirements.

The investigator must ensure that each study subject, or his/her legally acceptable representative, is fully informed about the nature and objectives of the study and possible risks associated with participation. The investigator, or a person designated by the investigator, will obtain written informed consent from each subject or the subject's legally acceptable representative before any study-specific activity is performed. The informed consent form used in this study, and any changes made during the course of the study, must be prospectively approved by both the IRB/IEC and the Sponsor before use. The investigator will retain the original of each subject's signed consent form.

2. INVESTIGATORS AND STUDY ADMINISTRATIVE STRUCTURE

Details on the administrative structure of the study (e.g., investigator, coordinating, steering committee, administration, monitoring and evaluation committees, institutions, statistician, central laboratory facilities, external service provider (ESP or CRO), or clinical study supply management) will be maintained in the Sponsor's Study Master File throughout the study for inclusion in the clinical study report.

3. STUDY OBJECTIVES

3.1. Primary Objective

• The primary objective is to explore the effects of a 4-6-week (28-42 days depending on subject availability for last testing day) intervention utilizing a novel health application (Pro2col Health) on daily activity, nutritional awareness, and numerous health outcomes in overweight but otherwise healthy subjects.

3.2. Secondary Objectives

- To assess subjective indications of depression using the PHQ-9 Scale.
- To assess subjective indications of quality of life, using the SF-36 Health Survey.

3.3. Exploratory Objectives

• Record any adverse event (AE) experienced by study subjects after enrollment in the digital application.

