5. INVESTIGATIONAL PLAN

5.1. Overall Study Design and Plan

This is a non-blinded randomized controlled pilot trial conducted over up to 8 weeks. Week 0 will involve baseline measurements and enrollment, Weeks 1-6 constitute the intervention, and Week 7 to 8 is reserved for post-testing. The study will enroll up to 200 participants, with a minimum of 50 participants who meet the inclusion criteria, and a minimum target of 20 participants completing the study in each group (experimental and control).

Participants will be recruited from across the United States using a decentralized electronic database. The study will include individuals aged 21-60 with a BMI \geq 25 (overweight) and \leq 35. Additionally, qualified subjects must have current daily activity records that show an average daily step count under 5,000. Participants must also be free of disease and must own either a personal smartphone device with the Apple Health or Google Fit application. Finally, participants must be willing to keep their device with them at all times to ensure accurate activity tracking.

Following baseline testing and enrollment in the study, participants will be randomly assigned to either the control (CON) or experimental (PRO) group. The control group will receive subject-facing materials depicting current general activity recommendations as published by the American Heart Association (AHA) and current dietary guidelines provided by the United States Department of Agriculture (USDA). The experimental group will be enrolled in the Prime Health Technologies software (Pro2col), which provides a digital diagnostic score to calculate healthspan and biological age, along with AI and group community-based coaching dynamics. Subjects will be assigned a 6 week progressive protocol targeting improvements in daily activity levels, nutritional awareness, and overall lifestyle risk factors. Both groups will then be monitored by study staff throughout the duration of the intervention period with post-testing taking place following the last week of the experiment.

Due to the remote nature of subject recruitment, no in-person facility visits are required for participants.

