7.3. INTERVENTION

Subjects will follow their assigned condition for 6 weeks. Subjects in the control group will be monitored by study staff but otherwise uninstructed in regard to activity and nutrition. Their adherence to the provided educational materials is entirely up to them. The experimental group will be initiated into a 4-6-week (28-42 days depending on subject availability for the last testing day) progressive protocol on the Pro2col app. They will receive daily updates, notification, and education regarding healthy habits such as exercise, hydration, and improved nutrition practices. An AI coach will be responsible for providing instructions and feedback to all application users.

7.4. **POST-TESTING**

Subjects who complete the 4-6-week (28-42 days depending on subject availability for last testing day) intervention and continue to be eligible for this study will then complete post testing. Subjective questionnaires will be provided to assess items such as current activity levels, nutrition habits, and lifestyle factors related to health and wellness. Enrolled and randomized subjects will also receive a blood pressure cuff and digital scale to record blood pressure and bodyweight/body composition, respectively. Moreover, subjects will complete electronic calculations to estimate their healthspan and biological age. Finally, subjects will perform three physical fitness tests, including:

- Timed one mile walk/run
- Push-ups (or modified push-ups for women) to exhaustion
- Chair get-ups to exhaustion

Finally, upon completion of the study (or early withdrawal), subjects will be directed to delete the investigational application from their smart device, and no further data will be collected.

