9. ADVERSE EVENT REPORTING

9.1. Introduction

All observed or volunteered adverse events regardless of treatment group or suspected causal relationship to the INP(s) will be reported as described in the following sections.

For all adverse events, the investigator must pursue and obtain information adequate both to determine the outcome of the adverse event and to assess whether it meets the criteria for classification as a serious adverse event requiring immediate notification to the Sponsor or its designated representative. For all adverse events, sufficient information should be obtained by the investigator to try to determine the causality of the event. For adverse events with a suspected causal relationship to the experimental product, follow-up by the investigator is required until the event or its sequel resolve or stabilize at a level acceptable to the investigator, and Sponsor concurs with that assessment.

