9.2. Reporting Period

Serious adverse events require immediate notification within **24 hours** to the IRB and its designated project manager. When reporting a serious adverse event, the investigator or designee completes the SAE form with as much information as possible however, at a minimum the Subject ID, Name of INP, SAE, and Name of person reporting the event.

All adverse events (serious and non-serious) must be collected on the subject's case report form (CRF) from the time the subject signed informed consent through the last subject visit.

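### Adverse events have two different start points and are captured passively in an unblinded remote trial where only the app arm has described daily contact, so counts may not be comparable between arms (minor)

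*Combined protocol and SAP*

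**What the plan says.** **Start point.** Section 3.3 (Exploratory Objectives) reads "Record any adverse event (AE) experienced by study subjects after enrollment in the digital application". Section 9.2 (Reporting Period) requires all AEs, serious or not, to be collected "from the time the subject signed informed consent through the last subject visit".

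**Who is in the application.** Section 5.1: "The experimental group will be enrolled in the Prime Health Technologies software", after baseline testing and randomisation. Controls (CON) receive published activity and dietary materials. Section 5.2.1, however, asks every subject to be willing to download the application and connect it to their phone's health data.

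**How events are found.** Section 9.1 covers "All observed or volunteered adverse events regardless of treatment group". Section 8.2 relies on self-report and observation, and 6.5 on spontaneous or self-reported events. Section 8.1 describes the observed route as an examination by the investigator. Section 5.1 requires no in-person visits, and 6.4 says that neither staff nor participants are blinded.

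**Contact by arm.** Section 7.3 says of PRO: "They will receive daily updates, notification, and education regarding healthy habits". Sections 5.1 and 7.3 provide for staff monitoring of both arms but give neither its frequency nor its content.

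**Reporting of results.** Section 10.3.3 tabulates the number and percentage of subjects with AEs in a Safety population that is not defined, by severity and by relation to treatment.

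**Serious events.** Section 9.1 refers to events "requiring immediate notification to the Sponsor or its designated representative". Section 9.2 sends the 24-hour notice "to the IRB and its designated project manager".

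**The concern.** Two features could make AE counts hard to read.

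First, the objective and the collection rule start the clock at different moments. If 3.3 is taken literally and 5.1 decides who is enrolled in the application, controls have no start point. Events during the baseline mile, push-ups and chair get-ups would also fall before the window in PRO.

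Second, passive capture depends on subjects thinking to report. An arm that hears from the study every day may report more readily than one that does not, and in an open-label trial expectations about the intervention may add to this. An excess in PRO could then reflect reporting, and similar counts could hide a real difference. Section 9.6 handles events of unknown cause as related to the product, so uneven reporting could also carry into the relatedness table.

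The AE summary is the trial's only planned safety evidence on a programme that combines time-restricted eating, reduced calories and increased activity. Events never reported during the trial cannot be recovered at analysis.

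**Working it through.** The documents state no AE rate, reporting probability or contact frequency, so there is no plan figure to reproduce. The check sets the sections side by side.

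1. **Are the start points different?** Yes. Section 3.3 begins at enrolment in the application and 9.2 at signed consent. By 5.1, consent and baseline testing come before enrolment in the application.

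2. **Does 3.3 exclude controls?** Not securely.
   - For exclusion: 5.1 enrols only PRO in the software.
   - Against: 5.2.1 asks all subjects to be willing to download it; 4.1 lists application-based outcomes at week 0; and Appendix 1 stores daily steps in the application and has application users perform the fitness tests. These imply that controls may have the application, possibly before the baseline tests.
   - Result: the meaning of enrolment in the application is ambiguous for controls.

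3. **Do the operative rules cover both arms?** Yes. Section 9.2 is mandatory for all subjects, 9.1 applies whatever the group, and 9.3 lists study procedures as a source of AEs. If Section 9 is followed, the window is the same in both arms.

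4. **Is capture passive?** Yes. Sections 6.5, 8.2 and 9.1 all describe observed, spontaneous, self-reported or volunteered events, and no section schedules an AE question. With no in-person visits required, investigator examination has limited reach.

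5. **Is contact unequal?** In part. Staff monitoring is planned in both arms. Daily messages and AI feedback are described for PRO; nothing equivalent is described for CON. No section gives the application or the AI coach a role in asking about or forwarding AEs.

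6. **Can the bias be sized?** No. Write the observed proportion in an arm as true risk × probability of being reported. With equal true risk in both arms,

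   observed ratio PRO/CON = (risk × report_PRO) / (risk × report_CON) = report_PRO / report_CON.

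   The true risk cancels, and neither reporting probability is in the documents. Any number put in would only restate the assumption; equal reporting gives a ratio of 1.

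7. **Is a between-arm table promised?** Not expressly. Section 10.2 says that baseline data are summarised by treatment; 10.3.3 has no such statement for AEs and plans no between-arm test.

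8. **When is randomisation?** Section 5.1 places it after baseline testing. Section 7.1 plans a consultation on the assigned condition, and 7.2 (baseline testing) already speaks of randomised subjects. The order decides which events count as pre-randomisation.

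9. **Do the serious-event recipients conflict?** Sections 9.1 and 9.2 name different recipients. Neither excludes the other, but the text does not say that both apply.

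**The case against.** The strongest reply is that Section 9, not a one-line exploratory objective, governs collection. It covers both arms from consent and includes events from study procedures, so the wording of 3.3 does harm only if staff set Section 9 aside. That stands: the start-point conflict is a drafting inconsistency to correct, not evidence of lost events. A reader might infer that control-arm or baseline-test events will go unrecorded; 9.1, 9.2 and 9.3 do not support that.

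The second reply is that staff monitor both arms throughout, that the daily contact in PRO is automated messaging on healthy habits with no stated AE function, and that controls are left uninstructed about activity and nutrition only, not about reporting events. That also stands. A reader might infer that the arms are prompted unequally for AEs, or that the safety comparison is already biased. The documents show unequal described contact and an unspecified AE query, which makes unequal reporting plausible but not established.

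What the reply does not answer is that the frequency and content of monitoring are unstated and no section says that it asks about AEs. It cannot be assumed to equalise capture.

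**Conclusion.** The point holds as a minor one. Sections 3.3 and 9.2 give different start points and must be reconciled. AE capture is passive in an unblinded remote trial, and daily contact is described for one arm only, so counts may not be like-for-like. This rests on two assumptions: that staff monitoring includes no standard AE question, since none is described, and that more frequent contact can raise reporting.

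No magnitude is given, because the documents supply no input for one. A reader might want to state a fold excess in PRO, or call the between-arm AE comparison invalid. Neither is supported: the first would repeat assumed reporting rates, and 10.3.3 does not expressly plan such a comparison. A reader of a randomised trial will nevertheless compare the arms, which is why the layout should be stated.

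The differing recipients of serious-event notice are a separate clarification. They may be cumulative; the text should say.

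**What to change.** - **Section 3.3:** align with 9.2, so that all AEs in both arms are recorded from informed consent to last contact.
- **Section 8.2:** add one AE question, identically worded, sent to every subject in both arms at the same fixed times through the same channel, outside the coaching application.
- **Section 10.3.3:** state that AEs are tabulated by randomised arm, with events before randomisation shown separately; define the Safety population; and make the timing of randomisation consistent across 5.1, 7.1 and 7.2 so that the split can be applied.
- **Sections 9.1 and 9.2:** reconcile who receives immediate notice of serious events.

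The cost is wording plus one short electronic item. Its schedule has to be written, because the protocol gives no monitoring timetable to attach it to. The downside is that more minor events will be recorded.

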4. OUTCOMES MEASURE

- 4.1. Primary Outcomes these measures will be taken at week 0 (pre) and week 7 (post)
 - Healthspan, as assessed via a digital score within the application software.
 - **Biological Age**, as assessed via an algorithm sourced within the application.
 - Lifestyle Risk Factors, as assessed via questionnaires within the application.
 - Energy and Vitality, as assessed via questionnaires within the application.
 - Strength and Endurance, as assessed by performance measures including a timed mile walk/run, push-ups to exhaustion, and chair get-ups to exhaustion.
 - Body Composition, as assessed via a previously validated digital scale.
 - Blood Pressure, as assessed via an electronic blood pressure cuff.
 - Lifestyle Habits, as assessed by specific interfaces within the application and guided by an AI "coach."
 - **Daily Steps**, as collected via the Apple Health or Google Fit application on the subject's pre-existing personal device.

4.2. Secondary Outcomes – these measures will be taken at week 0 (pre) and week 7 (post)

- **Depression**, as assessed by the previously validated PHQ-9 subjective questionnaire.
- Quality of Life, as assessed by the previously validated SF-36 subjective questionnaire.

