5.2.1 Inclusion Criteria

- Male or female, aged 21-60 years.
- A BMI categorized as overweight (≥ 25) but not stage II obesity (≤ 35)
- Daily steps < 5,000.

- Ownership of a smartphone device with either the Apple Health or Google Fit application.
- Willingness to carry their phone in their pocket or on their person at all times to track steps during study.
- Willing to download the Pro2col application and connect it with either the Apple Health or Google Fit application.
- Willingness to complete physical tasks including a timed one-mile walk/run, regular or modified push-ups to exhaustion, and chair get-ups to exhaustion.
- For the experimental group, subjects must be willing to follow the application protocol which is laid out later in this document.
- Able to read, understand, sign and date the informed consent document (English only)
- Able and willing to comply with the scheduled visit(s) and study requirements.

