6.2. Identity of Experimental Condition

The Experimental Condition involves the use of a novel smartphone application. This application provides a digital diagnostic score to calculate healthspan and biological age, along with AI and group community-based coaching dynamics. Subjects will be assigned a 4-6-week (28-42 days depending on subject availability for last testing day) progressive protocol designed to implement lifestyle changes and solidify adherable practices including the following:

- Daily practice of intermittent fasting, eating within a time restricted eating window ranging from 8 to 12 hours.
- Increased daily steps.
- Increased awareness of hydration practices.
- Journaling
- Adherence to a lower carbohydrate, higher-protein diet.
- Improved exercise habits.
- Stress management
- Sleep habits
- Improved lifestyle risk factors, like smoking and alcohol intake

The above factors are individualized based on subject responses to questionnaires within the application. An AI-based coach and application algorithms will then send users push notifications to improve adherence to their new lifestyle factors as well as provide feedback for their logged data entries. Specifically, the application users will be required to connect the Pro2col application with either the Apple Health or Google Fit application so that necessary data can be transmitted between these applications without user input. The application creates a personalized protocol by using responses from the embedded health questionnaire to establish baseline figures that the user will improve upon. For example, if a user reports walking between 4,001-5,000 steps daily, their program will start them at 4,000 steps in week 1, gradually increasing each week until they reach the program's goal (e.g., 10,000 steps). Below are the key elements used to generate an individualized protocol, with specific goals for this user:

Steps Goal: 10,000 Steps

Incremental Approach: Starting from the user's baseline, steps will gradually increase each week to reach the target of 10,000 steps over a 4-6-week period (28-42 days depending on subject availability for the last testing day).

Example:

Week 1: Starting at the baseline (e.g., 4,000 steps)

Week 2: 5,200 steps

Week 3: 6,400 steps

Week 4: 7,600 steps

Week 5: 8,800 steps

Week 6: 10,000 steps

Calorie Goal: Moderate Fat Loss

Caloric intake will be reduced on average by 250 calories from basal calorie needs.

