7.5. Subject Withdrawal and Early Termination

Subjects may withdraw from the study at any time at their own request, or they may be withdrawn at any time at the discretion of the investigator or Sponsor for safety, behavioral, or administrative reasons. Every effort should be made to document the subject outcome, if possible. The investigator should inquire about the reason for withdrawal, request the subject return for a final visit, and if applicable, follow-up with the subject regarding any unresolved adverse events.

If the subject withdraws from the study and also withdraws consent for disclosure of future information, no further evaluations will be performed, and no additional data will be collected. The Sponsor may retain and continue to use any data collected before such withdrawal of consent.

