Endurance: Endurance will be assessed using a one mile walk time. Subjects will perform this assessment at their own determined pace, which is obviously restricted by their physical ability. Running is allowed, but not all subjects will be able to run the full mile. Thus, walking is allowed in this assessment.

Lower Body Strength: Lower body strength will be assessed by chair get-ups to concentric muscle failure. Briefly, subjects must use a chair or a related sturdy surface that reaches the height of their patella. They must fully sit and return to start for each repetition. They will

continue to perform get-ups to concentric muscle failure. This number will be reported to assess their lower body strength.

Body Composition

Body composition will be measured using a previously validated digital scale (RENPHO Smart Scale) that will be delivered to participants upon enrollment in the study. The scale uses bioelectrical impedance to estimate body composition. This involves a low level electrical current being sent through the body; the user cannot feel, hear, or otherwise sense this electrical current. The rate at which the current passes through the body is then input into an algorithm to estimate body composition based on known electrical current rates in human body tissue.

Body composition will also be estimated by questions embedded within the application and a corresponding algorithm.

Blood Pressure

Blood pressure will be measured using a previously validated electronic blood pressure cuff (Oklar Cuff Model C02) that will be delivered to participants upon enrollment in the study. The blood pressure cuff is capable of executing blood pressure measurements with minimal input from the user. Blood pressure is reported as systolic over diastolic, and the user will input these numbers into the application questionnaire.

Daily Steps

Daily steps will be assessed using communication between the Pro2col application and the user's Apple Health or Google Fit application. Apple Health and Google Fit both collect daily step counts by way of accelerometry, gyroscopy, and global positioning systems (GPS) and these data will be transferred to and housed within the Pro2col application.

Depression

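### Daily steps are recorded throughout the study, but the plan states a use only for the week-0 and week-7 values; a baseline-adjusted model of weekly mean steps would use the rest and retain early leavers.

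*Combined protocol and SAP*

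**What the plan says.** - **Timing.** Section 4.1 lists Daily Steps among the primary outcomes and gives one schedule for all of them: "Primary Outcomes these measures will be taken at week 0 (pre) and week 7 (post". Section 5.1 adds: "Weeks 1-6 constitute the intervention, and Week 7 to 8 is reserved for post-testing".
- **Programme length.** Sections 3.1 and 7.4 describe a "4-6-week (28-42 days depending on subject availability for last testing day) intervention", and 6.2 and 7.3 give the same range. Section 7.3 also says that subjects follow their condition for 6 weeks.
- **Step recording.** Section 5.2.1 requires of every subject: "Willingness to carry their phone in their pocket or on their person at all times to track steps during study". Appendix 1 (Daily Steps) says "Apple Health and Google Fit both collect daily step counts by way of accelerometry, gyroscopy, and global positioning systems (GPS") and that "these data will be transferred to and housed within the Pro2col application". Section 6.2 has application users connect the apps "so that necessary data can be transmitted between these applications without user input".
- **Analysis.** Section 10.3.1 tests changes with paired t tests. It names no weekly or repeated-measures analysis, no analysis set for efficacy and no missing-data rule.
- **Step measure.** Neither 4.1, the procedure lists in 7.2 and 7.4, nor Appendix 1 says how many days a step value covers or what makes a day valid.
- **Early leavers.** Section 7.4 limits post-testing to subjects who complete the intervention. Section 7.5 says, of subjects who withdraw consent, "The Sponsor may retain and continue to use any data collected before such withdrawal of consent".
- **Sample size.** Section 10.1 bases 50 subjects on an effect size of 0.8 for habits, with daily steps as its example.

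**The concern.** Daily activity comes first in the primary objective, and steps are the example on which the sample size rests. Steps are also the one primary outcome that the documents describe as recorded daily by the phone, yet 4.1 schedules them like the fitness tests, once before and once after.

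Two things follow. The weeks in which the programme acts have no stated place in the analysis. And a subject who leaves during week 5, with four full weeks of counts held, probably drops out of the step comparison altogether. If leaving is related to activity, an analysis of completers alone can also be biased.

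**Working it through.** **1. The plan's own figure.** The documents give d = 0.8 and a 0.05 significance level. I assume two-sided testing, 80% power and 1:1 allocation, none of which is stated. Then n per arm = 2(1.960 + 0.842)²/0.8² = 24.5, so 25 per arm and 50 in total. The stated 50 is reproduced (the t-test version gives 52). Two-sample t-test power is 0.791 at 25 per arm and 0.693 at the minimum of 20 completers per arm in 5.1.

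**2. Precision of a two-week mean against one week.** The documents give no between-week correlation ρ, so I take 0.5 to 0.8 as an assumption, equal for all pairs of weeks, with equal variances and one baseline week. The variance of a k-week mean given baseline is (1 + (k−1)ρ)/k − ρ².

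| ρ | k = 1 | k = 2 | ratio | 50 subjects act as |
|---|---|---|---|---|
| 0.5 | 0.750 | 0.500 | 0.667 | 75 |
| 0.6 | 0.640 | 0.440 | 0.688 | 73 |
| 0.7 | 0.510 | 0.360 | 0.706 | 71 |
| 0.8 | 0.360 | 0.260 | 0.722 | 69 |

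On unadjusted change scores the ratio is (1 + 1/2)/2 = 0.75 for any ρ, so 50 act as 67.

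**3. Allowing for signal.** The example in 6.2 rises from 4,000 to 10,000 steps, with weekly gains of 0, 1,200, 2,400, 3,600, 4,800 and 6,000.
- Weeks 5-6 average 5,400, which is 90% of the final gain. If week 7 holds the week-6 level, equivalent n is multiplied by 0.9² = 0.81: 50 × 0.81/0.667 = 61 down to 50 × 0.81/0.722 = 56. On change scores it is 50 × 0.81/0.75 = 54.
- Weeks 1-6 average 18,000/6 = 3,000, which is 50% of the final gain. On change scores the variance ratio is (1 + 1/6)/2 = 0.583, so d = 0.8 × 0.5/√0.583 = 0.52. Power at 20 per arm is then 0.365, against 0.693 for one week at the full gain. For weeks 5-6, d = 0.8 × 0.9/√0.75 = 0.83 and power is 0.726.
- If the post value already averages two weeks (5.1 reserves weeks 7 to 8), the variance gain in step 2 is nil.

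**4. What early leavers add to the week-7 contrast.** Steps 2 and 3 concern a late-programme mean. With complete data, a model with an arm-by-week term does not sharpen the week-7 contrast; the added weeks help it only through subjects who lack week 7.
- As an illustration, take 50 enrolled and 40 completing, with the 10 leavers holding four weeks each.
- Given baseline, the correlation between weeks is r = ρ/(1 + ρ), or 0.333 to 0.444. Four weeks explain R² = 4r²/(1 + 3r), or 0.22 to 0.34, of the week-7 variance.
- Relative to completers only, the variance is 1 − 0.2R², or 0.956 to 0.932. The 40 completers then act as about 42 to 43.

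**The case against.** The strongest reply is that the documents do not exclude use of the programme weeks. Section 4.1 says when measures are taken, not how many days a step value spans. Section 5.1 shows that step averages can be read from device history, and the counts are stored. This stands: a reader might infer that six weeks of data are discarded, but the documents show only that no use is stated. The length is also not a firm six weeks, given the 28-42-day wording.

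A reader might also infer that week 7 mixes the programme effect with decay after coaching. The documents do not support this. Section 7.4 has subjects delete the app only on completion or early withdrawal, and the 28-42-day wording may let the programme run up to the testing day.

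Nor is it stated that an early leaver contributes nothing. Section 7.5 asks the investigator to request a final visit, and no analysis set is defined. Exclusion is likely, not certain. The 20% loss implied by 40 of 50 is not a bound, because both numbers are minimum targets and up to 200 may enrol.

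Finally, a measure after the programme is a legitimate target for a pilot that aims at lasting habits. Making programme weeks the headline would change the question asked, and if programme length differs between subjects, each subject's last two weeks could be different study weeks in the two arms. I accept this, and week 7 should remain the main contrast. What survives is that step data described as held have no planned use, and that the step value is undefined.

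**Conclusion.** The point holds as a cheap improvement to the analysis, not as an error that invalidates the plan. Daily step counts cover the programme, but only week 0 and week 7 have a stated role, and subjects without week 7 are likely to be lost from the step analysis.

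The size is modest and rests on assumed correlations of 0.5 to 0.8. For a late two-week mean, 75 to 69 equivalent subjects is a ceiling, because it counts variance and ignores signal; 61 to 56 applies on the example ramp with week 7 at the week-6 level. For week 7 itself the added precision is small, about two to three subjects in the illustration, so the better reason is that early leavers are kept under a weaker assumption than a completers-only comparison needs. All of this depends on control-arm step histories reaching the trial. Sections 5.2.1 and Appendix 1 imply that they do, but 5.1 enrols only the experimental group in the software and no control-arm route is described.

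**What to change.** In 4.1 and 10.3.1:

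1. Define the step measure: weekly mean steps per subject over a stated window with a valid-day rule, using the same study weeks in both arms.
2. Analyse all recorded weeks, including the post-test week, in a mixed model with arm, week, arm-by-week, baseline mean steps and a subject random effect.
3. Keep the week-7 between-arm contrast as the main step result.
4. Add a late-programme mean, for example the last two intervention weeks common to both arms, as a pre-specified supporting contrast. Do not use a plain six-week mean.
5. Confirm and describe how control-arm step histories are transferred.
6. Reconcile the 28-42-day passages (3.1, 6.2, 7.3, 7.4) with the 6-week and week-7 passages (4.1, 5.1, 7.3), since the week definitions depend on them.

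The cost is analysis wording and some mixed-model programming in SPSS. No new data are needed if item 5 is confirmed. The model relies on a missing-at-random assumption, which should be stated.
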